#### **5.3.1.11. Effectiveness (Responder-based): MenABCWY**

See Section 5.3.1.2. If the co-primary effectiveness objectives for rMenB+OMV NZ are met (Sections 5.3.1.1 through 5.3.1.6), then the effectiveness (responder-based) for MenABCWY will be evaluated at 95% CI.

### 5.3.2. Additional considerations

Analyses of the primary effectiveness and immunogenicity objectives will be repeated by age group (10-17 years of age and 18-25 years of age), race, sex, region (US/ ex-US), and subjects with and without a previous MenACWY vaccination (primed and unprimed).

#### 5.3.2.1. Vaccine effectiveness (Test-based): rMenB+OMV NZ - 3 doses (0,2,6-months schedule)

The SAS code to analyse the Vaccine effectiveness (Test-based): rMenB+OMV NZ - 3 doses (0,2,6-months schedule) objective is specified below. Treatment, region, age category, previous ACWY vaccination, and strains will be modelled as fixed effect. To account for a possible over-dispersion, the DSCALE option in the model statement will be evaluated first. The DSCALE will be kept in the model only if the F-statistics for the DSCALE parameter is significant ( $p<0.05$ ). The following SAS code will be used for the VE calculation:

```

ods trace on;
ods output GEEEmpPEst = genmod_stats
CONVERGENCESTATUS = converge ;

PROC GENMOD data=dataset descending;
class trtgrp strain region agecat previousACWY subject_id ;
model outcome = trtgrp strain region agecat previousACWY / dist= bin
link= log DSCALE;
repeated subject = subject_id / type= CS withinsubject= strain;
estimate 'MenB026-ACWY' trtgrp 1 0 0 0 0 -1/ alpha=0.025 exp;

/*trtgrp R is MenB0,2,6 and trtgrp W is ACWY*/

run;

ods output close;

data genmod_stats;
set genmod_stats;
where parm = 'trtgrp' and level1 = '1';
rr = exp(estimate);
ub = exp(uppercl);
ve = (1 - rr)*100 ;
ve_ll = (1 - ub) * 100 ;
if ve_ll > 65 then success = 1 ;
else success = 0 ;
run;

```

where outcome represents the Bernoulli distributed outcome without bactericidal activity at a 1:4 dilution (i.e. response is 1 if titre < 4, and 0 if titre  $\geq$  4), one month after the 3rd vaccination in MenB 0,2,6 and one month after the MenACWY vaccination for the ACWY arm, trtgrp indicates the vaccine groups, strain is the serogroup B strain variable, region is either US or ex-US, agecat is the age at enrolment (10-17 YoA or 18-25 YoA), and previousACWY is previous ACWY vaccination (y/n) at enrolment.

rr is the relative risk (RR), which is obtained from the estimated parameters from PROC GENMOD. Vaccine effectiveness (VE) is then derived as  $(1-rr)\times 100\%$ .

ub represents the upper bound of the 97.5% CI of the relative risk. ve\_ll is the lower bound of the 97.5% CI for VE, if the value is greater than 65%, then the Vaccine effectiveness (Test-based): rMenB+OMV NZ - 3 doses (0,2,6-months schedule) objective is successful.

**5.3.2.2. Effectiveness (Responder-based): rMenB+OMV NZ - 3 doses (0,2,6-months schedule)**

Not applicable

**5.3.2.3. Vaccine effectiveness (Test-based): rMenB+OMV NZ - 2 doses (0,6-months schedule)**

See Section [5.3.2.1](#), with the difference in the treatment arm:

```
PROC GENMOD data=dataset descending;
class trtgrp strain region agecat previousACWY subject_id ;
model outcome = trtgrp strain region agecat previousACWY / dist= bin
link= log DSCALE ;
repeated subject = subject_id / type= CS withinsubject= strain ;
estimate 'MenB06-ACWY' trtgrp 0 1 0 0 0 -1/ alpha=0.025 exp;

/*trtgrp S is MenB0,6 and trtgrp W is ACWY*/
run;
```

**5.3.2.4. Effectiveness (Responder-based): rMenB+OMV NZ - 2 doses (0,6-months schedule)**

Not applicable

**5.3.2.5. Vaccine effectiveness (Test-based): rMenB+OMV NZ - 2 doses (0,2-months schedule)**

See Section [5.3.2.1](#), with the difference the outcome data for group R is from one month after the 2nd vaccination instead of one month after the 3rd vaccination.

**5.3.2.6. Effectiveness (Responder-based): rMenB+OMV NZ - 2 doses (0,2-months schedule)**

Not applicable

**5.3.2.7. Lot-to-lot consistency: MenABCWY - ACWY component**

Not applicable

### 5.3.2.8. Immunological non-inferiority: MenABCWY vs. MenACWY

As a sensitivity analysis, a parametric model will be run. A generalized linear model with factors for vaccine group and randomization factors (i.e. region (US/ex-US), age category (10-17 YoA/18-25 YoA)) will be ran, with the Binary distribution and link function is identity, and outcome is 4-fold rise. If the lower limit of the two-sided 97.5% CI for the difference in percentage of subjects with 4-fold rise between the 2 groups (ABCWY (pooled) lots –ACWY) coming from the model is above -10%, also the sensitivity analysis has demonstrated non-inferiority. If the co-primary effectiveness objectives for rMenB+OMV NZ are met (Sections 5.3.1.1 through 5.3.1.6), then the above will be evaluated at 95% CI.

### 5.3.2.9. Vaccine effectiveness (Test-based): MenABCWY

See Section 5.3.2.1, with the difference in the estimate statement:

```
PROC GENMOD data=dataset descending;
class trtgrp strain region agecat previousACWY subject_id ;
model outcome = trtgrp strain region agecat previousACWY / dist= bin
link= log DSCALE ;
repeated subject = subject_id / type= CS withinsubject= strain ;
estimate 'MenABCWY-ACWY' trtgrp 0 0 1 1 1 -3/ alpha=0.025 exp
divisor=3;

/*trtgrp T, U, and V are the ABCWY-1, ABCWY-2, and ABCWY-3 lots and
trtgrp W is ACWY*/
run;
```

### 5.3.2.10. Effectiveness non-inferiority: MenABCWY vs. rMenB+OMV NZ

As a sensitivity analysis, a parametric model will be run. A generalized linear model with factors for vaccine group and randomization factors (i.e. region (US/ex-US), age category (10-17 YoA/18-25 YoA), previous MenACWY vaccination (y/n)) will be ran, with the Binary distribution and link function is identity, and outcome is bactericidal activity measured by enc-hSBA at 1:4 dilution. If the lower limit of the two-sided 97.5% CI for the difference in percentage of samples with bactericidal activity measured by enc-hSBA at 1:4 dilution between the 2 groups (ABCWY (pooled) lots –MenB) coming from the model is above -5%, also the sensitivity analysis has demonstrated non-inferiority. If the co-primary effectiveness objectives for rMenB+OMV NZ are met (Sections 5.3.1.1 through 5.3.1.6), then the above will be evaluated at 95% CI.

In addition to the comparison of MenABCWY vs the selected MenB schedule per Section 5.3.1.10, MenABCWY will be compared to the other MenB schedule/schedules, whichever is applicable in the same way as described in Section 5.3.1.10. If MenB 0,2 schedule is selected as comparator, in addition MenABCWY will be compared to Menb 0,6 and MenB 0,2,6 schedule. If MenB 0,6 schedule is selected as comparator, in addition MenABCWY will be compared to MenB 0,2,6 schedule. No success criterion is defined for these group comparisons.

**5.3.2.11. Effectiveness (Responder-based): MenABCWY**

Not applicable

**5.4. Secondary effectiveness and immunogenicity****5.4.1. Analysis of secondary effectiveness and immunogenicity planned in the protocol****5.4.1.1. Immunological non-inferiority: MenABCWY vs. rMenB+OMV NZ**

Analysis set: PPS will be the primary analysis population.

Statistical method: The percentages of subjects with 4-fold rise\* in hSBA titres against N. meningitidis serogroup B indicator strains (M14459, 96217, M13520 and NZ98/254 for fHbp, NadA, NHBA and PorA P1.4 antigens, respectively) at 1 month after the last vaccination for the ABCWY group (pooled lots) (Day 211, Month 7) and 1 month after the 3-dose vaccination series (Day 211, Month 7) in MenB\_0\_2\_6 group or 2-dose vaccination series (Day 211, Month 7) in MenB\_0\_6 group or 2-dose vaccination series (Day 91, Month 3) in MenB\_0\_2\_6 group and the corresponding exact 2-sided 95% CIs based on Clopper-Pearson method will be calculated [[Clopper](#), 1934]. The 95% CIs for the difference in percentages between ABCWY group (pooled lots) and MenB\_0\_2\_6 group and MenB\_0\_6 group will be constructed using the method of Miettinen and Nurminen [[Miettinen](#), 1985].

Non-inferiority criterion: Non-inferiority of MenABCWY vaccine for the proportion of subjects with 4-fold rise will be demonstrated if the lower limit of the 2-sided 95% CI for the difference in percentage of subjects with 4-fold rise between the 2 groups (ABCWY group (pooled lots) –selected MenB group) is above -10%.

\* For the MenB evaluation, the 4-fold rise per each indicator strain is defined as:

- a post-vaccination‡ hSBA titre  $\geq 4$  times the LOD or  $\geq$ LLOQ, whichever is greater, for subjects with a pre-vaccination hSBA titre  $<$ LOD
- a post-vaccination‡ hSBA titre  $\geq 4$  times the LLOQ for subjects with a pre-vaccination hSBA titre  $\geq$ LOD and  $<$ LLOQ, and
- a post-vaccination‡ hSBA titre  $\geq 4$  times the pre-vaccination hSBA titre for subjects with a pre-vaccination hSBA titre  $\geq$ LLOQ

‡ = post-2nd vaccination for 0,6 and 0,2 schedule and post-3rd vaccination for 0,2,6 schedule).

[Table 6](#) reads the LOD and LLOQ of hSBA titres against N. meningitidis serogroup B indicator strains used in the definition of 4-fold rise provided by the laboratory.

**Table 6 LOD and LLOQ of hSBA titres against *N. meningitidis* serogroup B indicator strains**

Strain	LOD	LLOQ
NZ98-254	CC1	
96217		
M14459		
M13520		

**5.4.1.2. Effectiveness by each of the endemic US *N. meningitidis* serogroup B strains**

Analysis set: FAS will be the primary analysis population. The ABCWY (pooled lots) group and the MenB group comparator that will be selected (ref: the footnote of [Figure 2](#)) will be used for the purpose of this analysis.

Statistical method: The VE per strain will be calculated as described in Section [5.3.1.1](#), using a generalised linear model with vaccine group, and randomization factors (i.e. region (US/ex-US), age category (10-17 YoA/18-25 YoA), previous MenACWY vaccination (y/n)) as independent variables, and alpha=0.05 leading to 95% CI. In case for a strain 100% response will be observed in both vaccine groups, VE against these strain will be assessed by calculating 95% CI for relative risk from raw proportions, and VE=1-RR.

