## CONFIDENTIAL

205416 [MENB REC 2ND GEN-038 (V72\_72)]

Statistical Analysis Plan Amendment 9

Objectives	Endpoints

Criterion:
 
Non-inferiority will be demonstrated if the LL of the 2-sided 95% CI for the group difference in percentage of subjects achieving a 4-fold rise** in hSBA titres against N. meningitidis serogroup B indicator strains is above -10%.
	
MenB_0_6 group) or 2-dose vaccination series (Day 91, Month 3 in MenB_0_2_6 group)† relative to baseline (Day 1, Month 0).

To assess the effectiveness of the rMenB+OMV NZ and MenABCWY vaccines against each of the randomly selected endemic US N. meningitidis serogroup B invasive disease strains as measured by bactericidal activity using enc-hSBA at 1 month after the 3-dose (0,2,6-months in MenB_0_2_6 group) and 2-dose (0,6-months in MenB_0_6 group, 0,2-months in MenB_0_2_6 group and 0,6-months in the ABCWY (pooled) group) vaccination series when compared to 1 month after the MenACWY vaccination.
	
The percentages of samples without bactericidal serum activity using enc-hSBA against each of the endemic US N. meningitidis serogroup B strains at 1 month after the:
 
 
3-dose vaccination series (Day 211, Month 7 in MenB_0_2_6 group)
 
2-dose vaccination series (Day 211, Month 7 in MenB_0_6 group)
 
2-dose vaccination series (Day 91, Month 3 in MenB_0_2_6 group)
 
last vaccination for the ABCWY group (pooled lots) (Day 211, Month 7), and
 
MenACWY vaccination (Day 31, Month 1 in ACWY group).
 

To describe the distribution of subjects by percentages of serogroup B invasive disease strains killed using enc-hSBA at 1 month after the 3-dose (0,2,6-months in MenB_0_2_6 group) and 2-dose (0,6-months in MenB_0_6 group, 0,2-months in MenB_0_2_6 group and 0,6-months in the ABCWY (pooled) group) vaccination series of rMenB+OMV NZ and MenABCWY vaccines.
	
The percentages of serogroup B invasive disease strains killed using enc-hSBA in each subject at 1 month after the:
 
 
3-dose vaccination series (Day 211, Month 7 in MenB_0_2_6 group)
 
2-dose vaccination series (Day 211, Month 7 in MenB_0_6 group)
 
2-dose vaccination series (Day 91, Month 3 in MenB_0_2_6 group), and
 
last vaccination for the ABCWY group (pooled lots) (Day 211, Month 7)
 

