#### 5.3.1.1. Vaccine effectiveness (Test-based): rMenB+OMV NZ - 3 doses (0,2,6-months schedule)

Analysis set: Per-protocol set (PPS) will be the primary analysis population

Statistical method: The VE is defined as  $1 - RR = (1 - \text{percentage of samples without bactericidal serum activity at 1:4 dilution in MenB group} / \text{percentage of samples without bactericidal serum activity at 1:4 dilution in the ACWY group}) \times 100\%$  and it will be analyzed using a generalised linear model with vaccine group, strain, and randomization factors (i.e. region (US/ex-US), age category (10-17 YoA/18-25 YoA), previous MenACWY vaccination (y/n)) as independent variables. Furthermore, a repeated statement will be used to estimate the variance of the RR including correlation within subject's responses to different strains. If the statistical model does not converge due to (one of) the factor(s), a model without this/these factor(s) will be fitted instead. The response variable of the model will be the Bernoulli distributed outcome without bactericidal activity at a 1:4 dilution (i.e. response is 1 if titre  $< 4$ , and 0 if titre  $\geq 4$ ), at 1 month after the last vaccination (Month 7) in the MenB group and at Month 1 for the ACWY group. Each subject will contribute with approximately 35 measures to this analysis, each of the measures corresponding to the response variable to one of the 35 strains randomly assigned to be tested with the samples available for that specific subject.

In order to obtain the VE measure which is a measure based on the relative risk (RR), a generalised linear model will be used with the Binary distribution and link function log in order to compute the log RR and the corresponding 97.5% CI. The obtained values will be exponentiated to obtain the RR and the corresponding 97.5% CI. The VE will be computed as  $100\% \times (1 - RR)$ . Effectiveness of rMenB+OMV NZ (0,2,6-months schedule) will be demonstrated if the lower limit of the two-sided 97.5% CI for VE between MenB and the ACWY group is above 65%.

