### 5.4.2.2. Effectiveness by each of the endemic US N. meningitidis serogroup B strains

The SAS code to analyse the Vaccine effectiveness (Test-based): rMenB+OMV NZ - 3 doses (0,2,6-months schedule) by strain is specified below. Treatment, and randomization factors (i.e. region (US/ex-US), age category (10-17 YoA/18-25 YoA), previous MenACWY vaccination (y/n)) will be modelled as fixed effect. To account for a possible over-dispersion, the DSCALE option in the model statement will be evaluated first. The DSCALE will be kept in the model only if the F-statistics for the DSCALE parameter is significant ( $p < 0.05$ ). The following SAS code will be used for the VE calculation:

```

ods trace on;
ods output GEEEmpPEst = genmod_stats
CONVERGENCESTATUS = converge ;

PROC GENMOD data=dataset descending;
class trtgrp region agecat previousACWY;
by strain ;
model outcome = trtgrp region agecat previousACWY / dist= bin link= log
DSCALE alpha=0.05;
estimate 'MenB026-ACWY' trtgrp 1 0 0 0 0 -1/ alpha= 0.05 exp;

/*trtgrp R is MenB0,2,6 and trtgrp W is ACWY*/

run;

ods output close;

data genmod_stats;
set genmod_stats;
by strain ;
where parm = 'trtgrp' and level1 = '1';
rr = exp(estimate);
ub = exp(uppercl);
ve = (1 - rr)*100 ;
ve_ll = (1 - ub) * 100 ;
if ve_ll > 65 then success = 1 ;
else success = 0 ;
run;

```

where outcome represents the Bernoulli distributed outcome without bactericidal activity at a 1:4 dilution (i.e. response is 1 if titre < 4, and 0 if titre  $\geq$  4), one month after the 3rd vaccination in MenB0,2,6 and one month after the MenACWY vaccination for the ACWY arm, trtgrp indicates the vaccine groups, strain is the serogroup B strain variable, region is either US or ex-US, agecat is the age at enrolment (10-17 YoA or 18-25 YoA), and previousACWY is previous ACWY vaccination (y/n) at enrolment.

rr is the relative risk (RR), which is obtained from the estimated parameters from PROC GENMOD. Vaccine effectiveness (VE) is then derived as (1-rr)x100%.

ub represents the upper bound of the 95% CI of the relative risk. ve\_ll is the lower bound of the 95% CI for VE, if the value is greater than 65%, then the Vaccine effectiveness (Test-based): rMenB+OMV NZ - 3 doses (0,2,6-months schedule) objective is successful.

In summary in case of convergence issue the following hierarchical decision tree will be applied

- Binary model including region, agecat, and previousACWY
- Binary model, excluding region, agecat, and previousACWY

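### The group sentences in 5.4.1.2 and 5.4.1.3 keep only ABCWY and one selected MenB schedule, in conflict with Table 1, the by-strain code and the method text of 5.4.1.3

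*SAP*

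**What the plan says.** **Objectives.** Among the secondary objectives in Table 1 (SAP Section 2) is effectiveness against each strain, for the 3-dose rMenB+OMV NZ series and for "2-dose (0,6-months in MenB_0_6 group, 0,2-months in MenB_0_2_6 group and 0,6-months in the ABCWY (pooled) group". The reference is stated: "vaccination series when compared to 1 month after the MenACWY vaccination". The matching endpoint lists the control as "MenACWY vaccination (Day 31, Month 1 in ACWY group". The next objective describes the percentage of strains killed per subject, for the same four vaccine series and without a control.

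**Groups to be analysed.** Section 5.4.1.2 restricts the by-strain analysis to two groups: "The ABCWY (pooled lots) group and the MenB group comparator that will be selected", with a pointer to the Figure 2 footnote. Section 5.4.1.3 carries the same sentence. That footnote (Section 6) picks a single MenB schedule according to which rMenB+OMV NZ objectives are met; if all are met, it picks 0,2.

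**Method.** Section 5.4.1.2 goes on: "The VE per strain will be calculated as described in Section" 5.3.1.1. The denominator of VE there is the "percentage of samples without bactericidal serum activity at 1:4 dilution in the ACWY group". The method paragraph of 5.4.1.3 lists all three MenB schedules and ABCWY.

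**Code.** Section 5.4.2.2 says that the SAS code for the 0,2,6 schedule "by strain is specified below". Its only contrast is "estimate 'MenB026-ACWY' trtgrp 1 0 0 0 0 -1/ alpha= 0.05 exp".

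**The concern.** The SAP gives different answers to a simple question: which vaccine series are analysed strain by strain, and against what? Table 1 says four series, each against ACWY. The group sentence says two groups, neither of them ACWY. The code says one series, 0,2,6, against ACWY. Two programmers working from this document could deliver different tables for the same secondary objective.

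The selection rule was written to choose the comparator for the MenABCWY non-inferiority objective on the B component. Neither analysis here is a non-inferiority comparison, so the rule has no evident purpose in them. Its effect is to make the schedules reported by strain depend on the primary results. Breadth across strains is close to the stated reason for the trial: Section 3.1 describes a commitment to confirm protection against diverse US serogroup B strains.

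**Working it through.** The SAP states no figure on this point, so the check is a comparison of texts, followed by counting.

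**Step 1: what Table 1 requires.** The by-strain endpoint has five group-timepoints: MenB 0,2,6 (Day 211), MenB 0,6 (Day 211), MenB 0,2 (Day 91, from the MenB_0_2_6 arm), ABCWY pooled (Day 211) and ACWY (Day 31). That makes four contrasts against ACWY. The strains-killed endpoint has the first four group-timepoints and no control.

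**Step 2: what the group sentence provides.** It names ABCWY pooled and one MenB schedule.
- By-strain VE: 5 − 2 = 3 group-timepoints are not named, namely ACWY and two MenB schedules.
- Strains killed: 4 − 2 = 2 are not named, both MenB schedules.

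**Step 3: what other text restores.**
- ACWY returns to by-strain VE through the definition in 5.3.1.1 and through the 5.4.2.2 contrast.
- The 5.4.2.2 code supplies 0,2,6 versus ACWY. It gives no contrast for MenB 0,6, MenB 0,2 or ABCWY.
- The 5.4.1.3 method paragraph lists all four series, directly against the sentence above it.
- Section 5.3.2.10 adds comparisons with the non-selected schedules, but only for the non-inferiority analysis of 5.3.1.10.
- Section 5.4.2.3 is marked not applicable, and Section 8 records no change from the planned analyses.

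**Step 4: by-strain VE under each possible selection**, with 110 strains in the panel.

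| Selected schedule | MenB schedules left out by the group sentence | Still without provision if the 5.4.2.2 code is also run |
|---|---|---|
| 0,2 | 0,2,6 and 0,6 | 0,6 (1 × 110 = 110 estimates) |
| 0,6 | 0,2,6 and 0,2 | 0,2 (1 × 110 = 110 estimates) |
| 0,2,6 | 0,6 and 0,2 | 0,6 and 0,2 (2 × 110 = 220 estimates) |

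Code and group sentence name the same MenB schedule only in the last row.

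**Step 5: why ACWY should be named.** VE = 1 − (failure rate in vaccine group / failure rate in ACWY). The documents give no failure rates, so assume 70–100% for ACWY, 15–25% for MenB and 15–20% for ABCWY.
- ABCWY versus ACWY: from 1 − 0.20/0.70 = 0.714 to 1 − 0.15/1.00 = 0.85.
- ABCWY versus MenB, the two named groups only: from 1 − 0.15/0.15 = 0 to 1 − 0.20/0.25 = 0.20 over the pairs tried.

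The two named groups cannot by themselves produce the quantity that the SAP calls VE.

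**The case against.** **The ACWY control is not lost.** A reader might infer from the group sentence that by-strain VE would compare MenABCWY with rMenB+OMV NZ. The mention of both vaccine groups later in 5.4.1.2, in the rule for strains with 100% response, invites that reading. The documents do not support it: the method sentence imports the ACWY denominator from 5.3.1.1, the code contrasts against ACWY, and Table 1 lists ACWY in the endpoint. What stands is that the group sentence does not name a group that the analysis needs.

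**The strains-killed distributions are not settled as missing.** The method paragraph of 5.4.1.3 lists all four series, so the defect there is a self-contradiction. No control is needed for that analysis.

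**A flat loss of 220 by-strain estimates is not established.** It holds if the group sentence alone governs, or if 0,2,6 is the selected schedule. When 0,2 is selected and the 5.4.2.2 code is run, 0,2,6 is produced and 110 estimates lack a provision. If the word group is taken to mean the whole MenB_0_2_6 arm at both timepoints, selecting 0,2 or 0,2,6 would likewise leave out only one schedule.

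**The selected comparator is not confined to 5.3.1.10.** Section 5.4.1.1 uses it too, for secondary non-inferiority on the indicator strains. Its use in a secondary analysis is therefore not an error in itself; the difficulty is that Table 1 does not apply it to these two objectives.

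**The stakes are limited.** Table 1 attaches no success criterion to either objective.

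These points narrow the concern. None of them reconciles the group sentences with Table 1, and no text restores all three MenB schedules for by-strain VE.

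**Conclusion.** The concern holds as a conflict within the SAP. Both group sentences are narrower than Table 1. The one in 5.4.1.2 also omits the name of the VE reference group and disagrees with the 5.4.2.2 code, which stays at 0,2,6 whichever schedule is selected. The one in 5.4.1.3 disagrees with its own method paragraph.

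If the group sentence governs, two of three MenB schedules are left out of each analysis. If the by-strain code is run as well, 0,2,6 is recovered for VE, and in the case where every rMenB+OMV NZ objective is met only 0,6 has no provision. This rests on taking a schedule, rather than an arm, as the unit selected, which is how the Figure 2 footnote words it.

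It would go too far to say that the plan fails to answer the two secondary objectives. On every reading MenABCWY and at least one MenB schedule are analysed for both, so coverage is partial and inconsistent. The matter should be corrected, but it does not affect any primary conclusion.

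**What to change.** - **5.4.1.2:** delete the selected-comparator sentence. State that MenB 0,2,6 (Day 211), MenB 0,6 (Day 211), MenB 0,2 (Day 91) and ABCWY pooled (Day 211) are each compared with ACWY (Day 31) for every strain.
- **5.4.1.3:** delete the same sentence and keep the four series that the method paragraph already lists.
- **5.4.2.2:** add by-strain contrasts for MenB 0,6 versus ACWY and ABCWY pooled versus ACWY, with the coefficients used in 5.3.2.3 and 5.3.2.9 and alpha 0.05.
- **MenB 0,2 by strain:** run it separately with group R's Day 91 outcome data, as 5.3.2.5 does for the primary analysis. Another ESTIMATE line in the same model will not work, because 0,2 and 0,2,6 share one treatment level. Stacking both timepoints would also treat two samples from one subject as independent, since the by-strain model has no REPEATED statement.

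The cost is SAP wording, some programming and extra table columns. The primary objectives already require enc-hSBA results at all five group-timepoints, so no new testing is needed.
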